### **Descriptive Summary**

The primary analysis will be proportion of evaluable patients across all age cohorts with HPA axis suppression, as observed from results of a cortisol response (ACTH stimulation) test at Day 30 (Post Treatment). Evaluable subjects are those that have both a baseline and end-of-study Cortisol Response Test results and have not been identified as having enrolled in the study previously. Patients found to have abnormal adrenal function after the baseline Cortisol Response Test will not be included in the evaluable patients for analysis.

#### **6.2.2 Secondary Analyses**

- Proportion of evaluable patients in each cohort with HPA axis suppression after the end of treatment.
- Pharmacokinetic parameters for desoximetasone at the end of treatment.
- Change from baseline/descriptive statistical analyses for the Physician Global Assessment (PGA) score at the end of treatment.

## STATISTICAL ANALYSIS PLAN

IND # 101789/ NDA # 204141

Protocol No. DSXS-1303

***TOPICORT® (desoximetasone) Topical Spray, 0.25% Pediatric HPA Axis study***

---

- Change from baseline/descriptive statistical analyses for clinical signs and symptoms (erythema, scaling, plaque elevation) of psoriasis at the end of treatment.

### 6.2.2.1 HPA Axis Suppression Analysis by Cohort

Similar to the primary analysis above, descriptive summary (frequency and proportion) of evaluable patients in each cohort with HPA axis suppression after the end of treatment will be presented.

### 6.2.2.2 Pharmacokinetic Analysis – PK Sampling Group Only

Concentrations of desoximetasone in plasma will be measured by the central laboratory using a fully validated analytical method. Pharmacokinetic and statistical analyses will be performed by Novum Pharmaceutical Research Services. The Statistical Analysis System (SAS®, Version 9.4 or higher) will be used for all pharmacokinetic and statistical calculations.

For Cohort 1, steady-state pre-dose (trough) plasma desoximetasone concentrations ( $C_{pre(Dx)}$ )  $x = 1, 8, 15, 22, 29$  will be measured from morning pre-dose blood draws at Visits 2-6 (Days 1, 8, 15, 22 and 29). At Visit 6 (Day 29), in addition to the pre-dose draw, patients will have blood collections following a dose applied in the clinic. The blood collection schedule will be as follows: 0 (pre-dose), 15 min, 30 min, 40 min, 50 min, 60 min, 1.5 hr, 2 hr, 3 hr, 4 hr, 6 hr, 8 hr, 12 hr ( $C_{post(D29),12hr}$ ) following the morning dose. Linear and semi-logarithmic graphs of each patient's plasma concentration-time profile for desoximetasone will be constructed using the actual times of sample collections.

For Cohort 2, steady-state pre-dose (trough) plasma desoximetasone concentrations ( $C_{pre(Dx)}$ ,  $x = 1, 8, 15, 22, 29$ ) will be measured from morning pre-dose blood draws at Visits 2-6 (Days 1, 8, 15, 22 and 29). At Visit 6 (Day 29), in addition to the pre-dose draw, patients will have blood collections following a dose applied in the clinic. The blood collection schedule will be as follows: 0 (pre-dose) 1 hr and 3 hr following the morning dose. Linear and semi-logarithmic graphs of each patient's plasma concentration-time profile for desoximetasone will be constructed using the actual times of sample collections.

If sufficient data are available and pending review of the individual pre-dose profiles, the approach to steady-state concentrations may be evaluated from the measurable morning pre-dose concentrations ( $C_{pre(Dx)}$ ) on Days 8, 15, 22 and 29, using Helmert contrasts comparing Day 22 and Day 29, Day 15 and the average of Days 22 and 29, and Day 8 and the average of Days 15, 22 and 29. The individual pre-dose profiles will be first reviewed visually to determine if the steady-state analysis is warranted and can be reliably assessed.

Graphical presentations of mean results will use the scheduled times of sample collections. A complete listing of the scheduled and actual times of sample collections for each patient and the concentration reported for each collected sample will be provided.

No concentration estimates will be provided for missing sample values. Any sample with a missing value will be treated as if the sample had not been scheduled for collection.

## STATISTICAL ANALYSIS PLAN

IND # 101789/ NDA # 204141

Protocol No. DSXS-1303

***TOPICORT® (desoximetasone) Topical Spray, 0.25% Pediatric HPA Axis study***

---

For the derivation of PK parameters for Cohort 1 on Day 29, plasma concentrations recorded as below the lower limit of quantitation (LLOQ) of 25 pg/mL (i.e., BLQ) will be handled per Sections 5.2.1.1, 5.2.1.2 and 5.2.3.1 of Novum's SOP 6102C (*Handling Below Lower Limit of Quantitation Data in Pharmacokinetic Studies*) and assigned a value of zero (i.e., 0) if they occur at the beginning or end of the 12-hour concentration-time profile and assigned a missing value if they occur in the middle of the PK profile for each patient. All BLQ values for  $C_{\text{pre(Dx)}}$  in Cohorts 1 and 2 will be assigned a value of zero.

Data from patients with missing concentration values (missed blood draws, lost samples, samples unable to be quantified) may be used if pharmacokinetic parameters can be estimated using remaining data points, otherwise data from these patients will be excluded from the final descriptive statistics.

For Cohorts 1 and 2 on Day 29, the peak exposure at steady-state ( $C_{\text{max-ss}}$ ) will be the observed maximum plasma concentration and the steady-state time to peak exposure ( $T_{\text{max-ss}}$ ) will be the collection time at which  $C_{\text{max-ss}}$  is first observed.

Steady-state area under the plasma concentration-time curve over the 12-hour dosing interval from time of dosing ( $t = 0$  hr) to the time of last sample at 12 hours post-dose ( $AUC_{\text{ss}}$ ) will be calculated by the linear trapezoidal method for Cohort 1 on Day 29. An AUC profile must have at least three consecutive measurable concentrations (i.e.,  $>$  LLOQ), including  $C_{\text{max-ss}}$ , to be considered evaluable. No  $AUC_{\text{ss}}$  and  $C_{\text{max-ss}}$  values will be reported for those PK profiles with fewer than three consecutive measurable concentrations. For those PK profiles with 0-concentration values at the end of the profile,  $AUC_{\text{ss}}$  will include the triangle area portion from  $t_z$  (time of last measurable concentration) to time of the first 0-concentration value at the end of the profile. If the 12-hour concentration is missing then  $AUC_{\text{ss}}$  will be calculated up to  $t_z$  but this value will not be included in the descriptive statistics for  $AUC_{\text{ss}}$ .  $AUC_{\text{ss}}$  will not be calculated for Cohort 2.

The apparent first-order terminal disposition rate constant ( $K_{\text{el}}$ ) will be estimated, when possible, from the negative of the slope of the regression line for the terminal ln-linear concentration-time values for Cohort 1 on Day 29. The values to be included in the regression lines will be selected by examination of each patient's semi-logarithmic concentration-time plot. The first-order terminal disposition half-life ( $T_{1/2}$ ) will be estimated as  $\ln(2)/K_{\text{el}}$ .

Descriptive statistics for all PK parameters (n, mean, SD, % coefficient of variation (%CV), minimum, median, maximum, geometric mean, geometric %CV) and for each time point (n, mean, SD, % coefficient of variation (%CV), minimum, median, maximum) will be reported by cohort. All BLQ concentration values will be replaced with 0 for the purpose of descriptive statistics for each time point.

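### A completeness rule written for AUCss also withholds Cmax-ss, and on its literal wording one BLQ value removes a Cohort 2 child's measured, usually low, maximum

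*Combined protocol and SAP*

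**What the plan says.** All of this is in SAP Section 6.2.2.2 (Pharmacokinetic Analysis – PK Sampling Group Only).

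- **Definition of Cmax-ss.** "For Cohorts 1 and 2 on Day 29, the peak exposure at steady-state" (Cmax-ss) "will be the observed maximum plasma concentration". No minimum number of values is attached.
- **AUCss.** The next paragraph concerns AUCss, which "will be calculated by the linear trapezoidal method for Cohort 1 on Day 29". It sets an evaluability condition: "An AUC profile must have at least three consecutive measurable concentrations", meaning values above the LLOQ, with Cmax-ss among them.
- **Withholding sentence.** For AUCss and Cmax-ss alike, no "values will be reported for those PK profiles with fewer than three consecutive measurable concentrations". No cohort is named.
- **Cohort 2.** AUCss "will not be calculated for Cohort 2". On Day 29: "The blood collection schedule will be as follows: 0 (pre-dose) 1 hr and 3 hr following the morning dose". That is three samples, against 13 in Cohort 1.
- **BLQ handling.** In Cohort 1 Day 29 profiles, BLQ values at either end are set to zero, and those in between are "assigned a missing value if they occur in the middle of the PK profile for each patient". A missing sample is treated as never scheduled. In the time-point summaries every BLQ value counts as 0.
- **Missed draws.** Patients with missing concentrations may still contribute wherever a parameter can be obtained from the samples that remain.

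**The concern.** A trapezoidal area needs several adjacent points. An observed maximum needs one. The SAP gives no reason for carrying the AUC condition over to Cmax-ss, and the sentence that does so can be read in two ways.

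- **Literal reading.** The rule covers every PK profile, including Cohort 2. A Cohort 2 child then gets a Cmax-ss only if all three samples exceed 25 pg/mL.
- **Narrow reading.** The paragraph opens with AUCss for Cohort 1, so the rule covers Cohort 1 only. Cohort 2 is untouched, but a Cohort 1 patient without three measurable values in a row still loses a measured maximum.

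On both readings exclusion depends on the quantity being summarised. BLQ values arise mainly in patients with low exposure, so low maxima are dropped and the summary is expected to move up.

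Cmax-ss is the only Day 29 peak-exposure parameter that Cohort 2 will have. On the literal reading its table would describe a smaller, higher-exposure group than the time-point table beside it, which keeps BLQ values as 0. Two programmers working from this text could also produce different Cohort 2 tables.

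**Working it through.** The plan states no figure on this point, so there is none to reproduce.

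**Step 1: what the rule does to three samples.** Each Cohort 2 sample (0, 1, 3 hr) is either measurable or BLQ, giving 2³ = 8 patterns. Only one, all three measurable, has three consecutive measurable values. One pattern is all BLQ and has no measured maximum. The other 8 − 1 − 1 = 6 contain a measured maximum that is withheld. Whether a BLQ value is scored zero or missing makes no difference, since at most two measurable values remain.

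For example, a profile of BLQ, 38, 30 pg/mL yields no Cmax-ss, while 26, 27, 26 pg/mL yields 27. The higher maximum is discarded because of its pre-dose value.

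A single missed draw has the same effect: two measured values define a maximum but can never make three in a row. That contradicts the SAP's allowance to use the remaining samples.

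**Step 2: how often, and how much.** The only inputs from the documents are the LLOQ of 25 pg/mL and the sample counts (3 and 13). Everything else is assumed:

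- lognormal concentrations with a flat profile and independent samples within a patient;
- between-patient CV of 80% or 120%, and within-patient CV of 40%. With log-SD = √ln(1 + CV²), these are 0.70, 0.94 and 0.39;
- a population median from 1.5 to 16 times the LLOQ.

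The ratio below is the geometric mean of reported Cmax-ss divided by that of all patients with at least one value above the LLOQ.

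Cohort 2, literal reading, for CV 80% / 120%:

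| Median (x LLOQ) | Measured maximum withheld | Ratio | Median withheld maximum (pg/mL) |
|---|---|---|---|
| 1.5 | 29.0% / 23.8% | 1.31 / 1.36 | 37 / 37 |
| 2 | 22.4% / 20.4% | 1.24 / 1.30 | 39 / 37 |
| 4 | 7.0% / 10.0% | 1.09 / 1.16 | 43 / 40 |
| 8 | 1.0% / 3.1% | 1.02 / 1.06 | 49 / 42 |
| 16 | 0.07% / 0.6% | 1.002 / 1.015 | 54 / 45 |

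At 1.5-4 x LLOQ, 65-80% of the withheld maxima are below 50 pg/mL, and at least 97% lie below the median reported one.

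Cohort 1, narrow reading, 13 samples. Mid-profile BLQ is set to missing and missing samples count as unscheduled, so at least 3 of the 13 values must be measurable:

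| Median (x LLOQ) | Withheld | Ratio |
|---|---|---|
| 1.5 | 7.7-8.2% | 1.09-1.12 |
| 2 | 4.3-5.9% | 1.06-1.09 |
| 4 | 0.6-1.9% | 1.01-1.04 |
| 8 | 0.03-0.35% | 1.001-1.009 |

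If a BLQ value instead breaks the run, the range at 1.5-4 x LLOQ becomes 2-19% withheld with a ratio of 1.03-1.27.

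**Step 3: what this means for about 12 patients.** The Synopsis gives about 12 PK patients for each cohort under Study Design, but for Cohort 1 only under Study Population and Study Conduct. For Cohort 2 on the literal reading at 1.5-4 x LLOQ:

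- expected number withheld: 12 × 0.070 = 0.8 to 12 × 0.290 = 3.5;
- chance that at least one is withheld: 1 − (1 − 0.070)¹² = 58% to 1 − (1 − 0.290)¹² = 98%;
- 95% CI factor for the geometric mean: 1.46-1.77. The shift of 1.09-1.36 therefore lies within sampling error.

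**Step 4: sensitivity.** With other assumptions (median 25-200 pg/mL, log-SD 0.8 or 1.0 between and 0.4 or 0.5 within patients, pre-dose at 0.7 of the later samples), 3-34% of patients lose a measured maximum and the ratio is 1.05-1.61. The direction is the same throughout, but the size is not stable.

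**The case against.** **The narrow reading is plausible.** The sentence sits in a paragraph about Cohort 1 AUCss, follows the definition of an AUC profile, and precedes a step that only applies where AUCss is calculated. If that is what was meant, no Cohort 2 child is affected. This stands as a possible reading. But the SAP names Cohort 1 elsewhere when it limits a rule and does not do so here, and it also refers to concentration-time profiles for Cohort 2. The Cohort 1 effect remains in any case, though it is small.

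**Naming Cmax-ss may be deliberate.** Declining to report a peak from one or two values near the LLOQ is a recognisable convention, and a maximum from few samples can understate the true peak. That is a fair reason to show the sample count. It does not justify a filter that removes mainly low values.

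**The remedy also selects.** All-BLQ patients still have no Cmax-ss. Under the model of Step 2 they are 17-23% of patients at 1.5 x LLOQ and 9-15% at 2 x. After the change the geometric mean is still 1.26-1.48 and 1.14-1.31 times that of all patients' true maxima. This is correct, but total selection falls: at 1.5 x LLOQ and CV 80% it goes from 1.26 × 1.31 = 1.65 to 1.26. A count of all-BLQ patients discloses the rest.

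**The sizes are assumed.** With pre-dose at half the later level, 42-64% of withheld maxima are below 50 pg/mL rather than 65-80%, while the share withheld rises to 18-46%. The magnitudes should be taken as illustrative.

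**Little depends on it.** Cmax-ss is secondary and descriptive, exclusions show in n, and the listed concentrations let a reader recover every withheld maximum. All true, and the reason the point is minor. However, n does not tell the reader that those missing were low.

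**Conclusion.** The concern holds, as a minor point. That the rule discards measured maxima follows from the SAP's own wording and sampling schedule. On the literal reading it does so for any Cohort 2 child with one or two BLQ results. On the narrow reading it does so for Cohort 1 patients without three measurable values in a row.

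The upward direction rests on one inference, that BLQ values cluster in low-exposure patients. The size rests wholly on the assumed distribution. The effect matters only if typical concentrations are within a few multiples of the LLOQ; at 8 x LLOQ it is small in Cohort 2 (1-3% withheld, ratio 1.02-1.06).

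The primary HPA-suppression proportion is untouched, and no decision stated in the plan uses mean Cmax-ss. Confidence is medium, because the intended scope of the sentence and the actual concentrations are both unknown.

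**What to change.** In SAP Section 6.2.2.2:

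1. Remove Cmax-ss from the withholding sentence and state that the three-consecutive-value condition applies to AUCss in Cohort 1 only.
2. Add wording such as: *Cmax-ss is reported as the observed maximum for each Cohort 1 or Cohort 2 PK patient with at least one quantifiable Day 29 concentration, including patients with a missed draw; the number of samples on which it is based is shown.*
3. Give the number of patients whose Day 29 samples were all BLQ (<25 pg/mL) beside the Cmax-ss summary.

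The cost is one deletion, one or two sentences and one count row in the table. No further samples are needed. The downside is that mean Cmax-ss may be lower and more variable, and a maximum based on few samples can understate the true peak, which is why the sample count must be shown.

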## STATISTICAL ANALYSIS PLAN

IND # 101789/ NDA # 204141

Protocol No. DSXS-1303

***TOPICORT® (desoximetasone) Topical Spray, 0.25% Pediatric HPA Axis study***

---

### 6.2.2.3 Physician Global Assessment (PGA) Score

At all Visits a visual inspection to confirm a diagnosis of chronic plaque psoriasis will be done. PGA scores will be assessed at each visit on a 5-point scale (Appendix B): 0=clear, 1=almost clear, 2=mild, 3=moderate, 4=severe, 5=very severe.

Frequency and percentage will be presented for PGA scores by cohort and study day.

Descriptive summary (n, mean, standard deviation, minimum, median and maximum) will be presented for PGA scores by cohort and study day as well as change from baseline to end of treatment. Baseline is defined as the PGA score at Day 1 (Visit 1).

PGA scores will be listed by cohort, patient and study day.

### 6.2.2.4 Clinical Signs and Symptoms of Psoriasis

At all Visits a visual inspection to confirm a diagnosis of chronic plaque psoriasis will be done.

Clinical signs and symptoms (erythema, scaling, plaque elevation) will be assessed at each visit on a 5-point scale: 0=clear, 1=almost clear, 2=mild, 3=moderate, 4=severe, 5=very severe.

Frequency and percentage will be presented for clinical signs and symptoms by cohort and study day.

Descriptive summaries (n, mean, standard deviation, minimum, median and maximum) will be presented for clinical signs and symptoms by cohort and study day as well as change from baseline to end of treatment. Baseline is defined as the clinical signs and symptoms at Day 1 (Visit 1).

Clinical signs and symptoms will be listed by cohort, patient and study day.

## 6.3 Safety Analysis

Safety analysis will be conducted on all patients who applied at least one dose of study drug.

### 6.3.1 Adverse Events

All the adverse events (AEs) reported throughout the study will be coded and classified according to the MedDRA (Medical Dictionary for Regulatory Activities) coding dictionary (Version 16.0 or higher). Each adverse event is to be evaluated for date of start and end, seriousness, severity, causal relationship with the study drugs, action taken and outcome.

All AEs will be listed by cohort and patient.

A summary table of the number and percent of patients with AEs by system organ class, preferred term, and cohort will be presented. Each patient will be counted only once within each preferred term.

## STATISTICAL ANALYSIS PLAN

IND # 101789/ NDA # 204141

Protocol No. DSXS-1303

***TOPICORT® (desoximetasone) Topical Spray, 0.25% Pediatric HPA Axis study***

---

A frequency summary table of the number of AEs by system organ class, preferred term, severity, and cohort will be presented. Severity will be classified as “Mild”, “Moderate”, or “Severe”.

Similarly, a frequency summary table of the number of AEs by system organ class, preferred term, and relationship to a study drug, and cohort will be presented. Relationship to a study drug will be classified as “Not Related” or “Related” where “Related includes “Possible”, “Probable”, or “Definite”.

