| Criteria for Evaluation | 
Primary Outcome Measures:
 
Hypothalamic Pituitary Adrenal (HPA) Axis Response to Cosyntropin demonstrating the absence or presence of adrenal suppression at the end of the treatment
 
Secondary Outcome Measures:
 
 
• Changes on the Physician Global Assessment (PGA) score at the end of treatment.
 
• Changes on the Clinical Signs and Symptoms (erythema, scaling, plaque elevation) at the end of treatment.
 
• Pharmacokinetic parameters for desoximetasone at the end of treatment.
 
   |
| Statistical Analysis    | 
Primary analysis:
 
 
• Proportion of patients in the study with HPA axis suppression following treatment with the study medication.
 
 
Secondary analyses:
 
 
• Proportion of patients in each cohort with HPA axis suppression following treatment with the study medication.
 
• The frequency, severity, and relationship to study drug for AEs will be used to evaluate the safety profile of the study drug.
 
• A descriptive analysis on changes in PGA and Clinical Signs and Symptoms.
 
 
Two planned interim analysis will be conducted following the end of the treatment periods for cohorts 1 and 2.
 |

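### The severity and relationship tables count adverse events only, so no planned summary gives the share of children with a related event or by worst severity

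*Combined protocol and SAP*

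**What the plan says.** SAP 6.3.1 describes one listing and three tables for adverse events.

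- Listing: "All AEs will be listed by cohort and patient".
- Table by patient: "A summary table of the number and percent of patients with AEs by system organ class, preferred term, and cohort will be presented". The counting rule attached to it is "Each patient will be counted only once within each preferred term". No rule is given for the system organ class rows or for an overall row.
- Table by severity: "A frequency summary table of the number of AEs by system organ class, preferred term, severity, and cohort will be presented".
- Table by relationship: "a frequency summary table of the number of AEs by system organ class, preferred term, and relationship to a study drug", again split by cohort. The SAP reduces relationship to two classes, related and not related.

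The attributes are recorded for every event: "Each adverse event is to be evaluated for date of start and end, seriousness, severity, causal relationship with the study drugs, action taken and outcome". SAP 6.3 sets the safety population as every patient dosed at least once. The synopsis makes the AE profile a secondary objective and says in its Statistical Analysis row: "The frequency, severity, and relationship to study drug for AEs will be used to evaluate the safety profile of the study drug".

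**The concern.** The counting unit changes between the first table and the other two. The first counts children and gives a percentage, but ignores severity and relationship. The other two carry severity and relationship but count events, so a child with repeated events contributes several times and no denominator is given.

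Two ordinary safety questions therefore have no planned summary: what share of children had at least one event judged related, and how children are distributed by worst severity. Elsewhere in this study the child is the unit for safety. The primary analysis is a proportion of patients, and the enrolment rule in the synopsis is a percentage of dosed subjects. Two interim analyses are also planned to evaluate safety, after Cohorts 1 and 2, and the planned tables would not give these shares there either.

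**Working it through.** The plan states no figure on this point to reproduce. The check compares the counting units and then asks how much the planned tables leave open.

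**Step 1. Units side by side (SAP 6.3.1).**

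| Output | Unit | Percent of patients? | Split by severity or relationship? |
|---|---|---|---|
| Patient table | children | yes | no |
| Severity table | events | no | severity |
| Relationship table | events | no | relationship |
| Listing | one entry per event, by child | no | not stated, but both are recorded per event |

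No row combines a count of children with either attribute.

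**Step 2. Size of the ambiguity in the relationship table alone.** The documents give no AE count, so assume six related events in a cohort. The number of children affected, x, can be any value from 1 to 6. The share is x/n. The exact (Clopper-Pearson) 95% limits are the 0.025 quantile of Beta(x, n−x+1) and the 0.975 quantile of Beta(x+1, n−x). The values of n are taken from the synopsis ranges of 20-40, 20-30 and 10-30.

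| n | x = 1 | x = 6 |
|---|---|---|
| 40 | 2.5% (0.1 to 13.2%) | 15.0% (5.7 to 29.8%) |
| 30 | 3.3% (0.1 to 17.2%) | 20.0% (7.7 to 38.6%) |
| 20 | 5.0% (0.1 to 24.9%) | 30.0% (11.9 to 54.3%) |
| 10 | 10.0% (0.3 to 44.5%) | 60.0% (26.2 to 87.8%) |

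The relationship table shows 6 in every cell.

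**Step 3. What the patient table adds.** It uses the same preferred term and cohort rows, so the two can be read together. For one preferred term in one cohort, let k be the children with that term, R ≥ 1 the related events and U the unrelated events. A child without a related event needs at least one unrelated event, so the number of children with a related event lies between max(1, k−U) and min(k, R).

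- If U = 0, both bounds agree whenever k ≤ R, which must then hold. The number is exactly k and there is no ambiguity.
- With R = 6 and k = 6, the lower bound falls to 1 only if 6−U ≤ 1, that is, U ≥ 5. Within a single term, the full range of 1 to 6 needs at least five unrelated events as well.

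**Step 4. Totals across terms.** Suppose the six related events fall under six different preferred terms in six different system organ classes, in a cohort of 40. The patient table shows 1 child (2.5%) in each of six rows, and the relationship table shows 1 event in each. These entries are the same whether one child had all six events or six children had one each. The share of children with any related event is then 2.5% or 15.0%, and the described tables do not say which. No overall row is described, and one for any AE would still mix related with unrelated events.

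The same reasoning applies to severity, with severe and milder events in place of related and unrelated.

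**The case against.** The strongest reply is that little is lost. Severity and causality are recorded for each event, all events are listed by patient, and at most 100 children are planned, so anyone holding the listing can count the shares. For single preferred terms the patient table bounds the answer and often fixes it. The primary safety outcome, HPA axis suppression, is already a patient proportion overall and by cohort, and a further AE table could be added later from the same data. All of this stands. It makes the point a small one, but it does not supply the missing summary.

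Three stronger readings are tempting, and the documents do not support them.

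- A reader might infer that the study will never report these shares. The listing allows them to be derived, so what is absent is a planned summary.
- A reader might infer that raw counts will mislead between cohorts because cohort sizes and visit numbers differ greatly. The size ranges overlap and allow equal cohorts, for example 30 in each. A ratio of 4 needs Cohort 1 at its maximum and Cohort 3 at its minimum (40/10). The contrast of six visits with three is between PK and non-PK children within Cohort 1. SAP 6.2.2.2 gives Cohort 2 PK children the same pre-dose draw days, and the synopsis leaves the Cohort 3 schedule to an amendment. Counting children would not remove an effect of visit number in any case, because more visits can raise patient incidence too.
- A reader might infer that the cohorts exist so that adverse events can be compared by age. The documents describe serial enrolment with a suppression rule and a PK review between cohorts. They plan no comparison of AEs between cohorts.

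**Conclusion.** The point holds as a minor reporting gap. The severity and relationship tables give event counts only, the patient table is split by neither attribute, and no planned summary gives the number and percent of children with a related AE or by worst severity. The synopsis nevertheless relies on both attributes to judge safety.

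In the assumed example of six related events among 40 children, the share affected could be 2.5% or 15.0%. The planned tables cannot separate these when the events are spread over different terms and organ classes. Within one term the ambiguity is smaller and may vanish. The six events are an assumption, and the real size depends on how often children have repeated events. No test, sample size, analysis population or data collection is affected.

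**What to change.** In both the severity and the relationship table of SAP 6.3.1, add the number and percent of children by cohort, with the SAP 6.3 safety population of that cohort as denominator. Count each child once per preferred term, once per system organ class and once overall, at worst severity in the first table and strongest relationship in the second. Print the denominator in each column heading, and keep the event counts as a second column.

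The cost is a few lines of SAP text and revised table shells. The data are already collected. The only downside is slightly wider tables.
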